#### **4.3.3 Estimand for Ratio to Baseline in NfL at Week 48 for Patients Assigned to OCR HD and Approved Dose Arms**

**Estimand:** The estimand is the mean change from baseline in NfL at Week 48 for RMS patients where no treatment discontinuation nor initiation of alternative MS treatment can occur, and within the OCR HD and approved dose arms, respectively.

**Estimator:** A Mixed model for repeated measures (MMRM) will be used to estimate mean change from baseline in NfL at Week 48 in the higher and approved dose of ocrelizumab arms. The MMRM will be fitted to each treatment arm separately. The dependent variable will be log base 10 of NfL, and the fixed effects in the model will include independent variables of visit (categorical variable with the following categories: Week 12, Week 24 and Week 48), log base 10 of NfL at baseline, the interaction between visit and log base 10 of NfL at baseline, and the randomization stratification factors. The model will not contain an intercept term; thus the regression coefficients of the visit levels will be an estimate of the mean change in log base 10 of NfL from baseline at the visit levels conditional on the baseline covariates. The baseline covariates in the model will also be centered, i.e., the mean of the variable over all patients in the study will be subtracted from the variable. Under this model parametrization, the estimate of the mean change from baseline at week 48 will be computed as  $10^{\text{(regression coefficient of Week 48)}}$ , which is based on an estimate of the geometric mean.

An unstructured variance–covariance structure will be applied to model the within-patient errors. The restricted maximum likelihood (REML) method will be used for estimation of variance components. The statistical significance of the estimated mean change from baseline will be calculated by using the Wald test.

In order to estimate the aforementioned estimand, the following **intercurrent event** handling strategies will be applied:

**Early discontinuation from study treatment:** All data after treatment discontinuation will be treated as missing following the hypothetical strategy.

**Initiation of an approved MS DMT medication:** All data after treatment discontinuation will be treated as missing following the hypothetical strategy.

**Pregnancy:** All data pre and post pregnancy onset will be included in the analysis following treatment-policy strategy.

**Death:** This is anticipated to be very rare, but in case of occurrence, it will be handled with the hypothetical strategy. That is, data after death will be treated as missing.

Missing data resulting from patients that withdraw their consent to participate in the study and/or a serious GCP breach will not be imputed.

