
 
To demonstrate that both the higher dose and standard dose of ocrelizumab can significantly reduce neurofilament light chain (NfL) from baseline
 
	
 
Population: as defined above.
 
Endpoint: Change from baseline in neurofilament light chain (NfL), i.e. ratio to baseline, at Week 48
 
Treatments: as defined above
 
Intercurrent events and handling strategies: 
 
–Early discontinuation from study treatment: Hypothetical strategy
 
–Initiation of an MS disease-modifying therapy (DMT) medication: Hypothetical strategy
 
–Pregnancy: Treatment-policy strategy.
 
–Death: Hypothetical strategy
 
 
 
Population-level summary measure: mean change in NfL from baseline, i.e. ratio to baseline, at Week 48 within each treatment arm
 

9-HPT = 9-hole peg test; cCDP12 = 12-week composite confirmed disability progression; cCDP24 = 24-week composite confirmed disability progression; CDP12 = 12-week confirmed disability progression; CDP24 = 24-week confirmed disability progression; CI9-HPT12 = 12-week confirmed increase of  $\geq 20\%$  from baseline in 9-HPT score; CIT25FWT12 = 12-week confirmed increase of  $\geq 20\%$  from baseline in T25FWT score; CIMSWs24 = 24-week confirmed  $\geq 8$  point increase in MSWS-12; cPIRA12 = cCDP12 independent of protocol-defined relapses; CWSDMT12 = Time to 12-week confirmed 4-point worsening in SDMT; DMT = disease-modifying therapy; EDSS = expanded disability status scale; HR = hazard ratio; MS = multiple sclerosis; MSWS-12 = 12-item Multiple Sclerosis Walking Scale; NfL = neurofilament light chain; RMS = relapsing multiple sclerosis; SDMT = Symbol Digit Modalities Test; T25FWT = timed 25-foot walk test.

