## **2. STATISTICAL HYPOTHESES AND SAMPLE SIZE DETERMINATION**

### **2.1 STATISTICAL HYPOTHESES**

The hypotheses to be tested for the primary estimand are:

- H0 (null hypothesis): There is no difference in the time to onset of cCDP12 between the higher and approved dose of ocrelizumab arms.
- H1 (alternative hypothesis): There is a difference in the time to onset of cCDP12 between the higher and approved dose of ocrelizumab arms.

This will be tested at the 5% significance level ( $\alpha = 0.05$ ) against two-sided alternatives.

Null and alternative hypothesis of similar form will be tested for all secondary efficacy endpoints, i.e., there is no difference (null hypothesis) vs there is a difference (alternative hypothesis) in endpoint between the higher and approved dose of ocrelizumab arms, except for NfL endpoints within each study arm where the hypotheses to be tested are:

- H0 (null hypothesis): There is no change in NfL from baseline at Week 48 within the higher or approved dose of ocrelizumab arms.

- H1 (alternative hypothesis): There is a change in NfL from baseline at Week 48 within the higher or approved dose of ocrelizumab arms.

The secondary efficacy estimands will be tested in the hierarchical order listed below, if the primary estimand and each preceding estimand have reached the significance level of 0.05:

- Time to onset of 24-week composite confirmed disability progression (cCDP24)
- Time to onset of 12-week confirmed increase in T25FWT (CIT25FWT12)
- Time to onset of cCDP12 independent of protocol-defined relapses (cPIRA12)
- Change from baseline in NfL at Week 48 for patients assigned to OCR HD arm
- Change in NfL from baseline at Week 48 for patients assigned to OCR approved dose arm
- Time to onset of 12-week confirmed disability progression (CDP12)
- Time to onset of 48-week composite confirmed disability progression (cCDP48)
- Time to onset of 12-week confirmed  $\geq 4$ -point worsening in Symbol Digit Modalities Test (CWSDMT12)
- Time to onset of 24-week confirmed  $\geq 8$ -point increase in 12-Item Multiple Sclerosis Walking Scale (CIMSWS24)
- Annual rate of percent change from baseline in total brain volume

The full description of the estimand attributes for the secondary estimands is provided in [Table 1](#).

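### SAP 4.3.3 models the log10 NfL level rather than its change from baseline, so the two confirmatory NfL tests do not test for a change

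*SAP*

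**What the plan says.** SAP Table 1 defines the endpoint as "Change from baseline in neurofilament light chain (NfL), i.e. ratio to baseline, at Week 48", and SAP 2.1 states the null hypothesis within each arm as "There is no change in NfL from baseline at Week 48". In the fixed sequence of SAP 2.1 the higher-dose arm is the fourth secondary test and the approved-dose arm the fifth.

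SAP 4.3.3 gives the estimator, fitted to each arm separately: "The dependent variable will be log base 10 of NfL, and the fixed effects in the model will include independent variables of visit". The other fixed effects are log10 baseline NfL, its interaction with visit, and the stratification factors. On interpretation it says: "The model will not contain an intercept term; thus the regression coefficients of the visit levels will be an estimate of the mean change". The baseline covariates are centred, meaning that "the mean of the variable over all patients in the study will be subtracted from the variable". No centring of the outcome is mentioned.

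The Week 48 result is obtained by raising 10 to the power of the Week 48 coefficient; in the SAP's words, "the estimate of the mean change from baseline at week 48 will be computed as" that quantity. Finally, "The statistical significance of the estimated mean change from baseline will be calculated by using the Wald test".

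**The concern.** Dropping the intercept and centring the covariates makes each visit coefficient the adjusted mean of the outcome at that visit. It does not turn a level into a change. The coefficients are mean changes only if the outcome is itself a change from baseline, and the text names the level. The same sentence uses the matching phrase, with the words for baseline added, to mean the baseline level, so the plain reading of the outcome is also a level.

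Under SAP 4.3, a later p-value counts as confirmatory only if the primary and every preceding secondary test reached 0.05. If the model is run literally, steps 4 and 5 are not tests of the stated null. They still decide whether CDP12, cCDP48, the SDMT endpoint, the MSWS-12 endpoint and brain volume can be claimed. The published ratio to baseline would also be a concentration.

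**Working it through.** The plan states no power, effect size or expected level for the blood NfL tests, so there is no figure of its own to reproduce. The check is algebra, followed by a simulation to show size.

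**Algebra.** Let b be a patient's log10 baseline NfL, b̄ the mean used for centring, y the log10 NfL at Week 48, and θ the Week 48 coefficient. The centred strata terms do not affect the argument.

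- Model as written: E[y] = θ + β(b − b̄).
- Subtract b from both sides: E[y − b] = (θ − b̄) + (β − 1)(b − b̄).
- The mean change is therefore θ − b̄. The coefficient as written is too large by b̄, and 10^θ = 10^b̄ × (true ratio to baseline).
- Testing θ = 0 tests whether the adjusted geometric mean at Week 48 equals 1 reporting unit.

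Example: with a baseline geometric mean of 10, b̄ = 1. A true 30% fall gives θ = 1 + log10(0.7) = 1 − 0.155 = 0.845, and 10^0.845 = 7.0. A fall to 0.70 of baseline would be reported as a sevenfold rise.

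**Inputs to the simulation.**

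- Arm sizes: 865 patients (SAP 2.2) split 2:1 (SAP 1.3.1), so 865 × 2/3 ≈ 577 and 865 × 1/3 ≈ 288.
- Log10 SD: 0.32, the CSF figure in section 6.1 of the substudy protocol (Protocol Appendix 18), borrowed for blood as an assumption.
- Not in the documents, so assumed: baseline geometric mean 5, 10 or 20 pg/mL; within-patient correlation 0.6; complete data.
- Model: the SAP's, with three visits and unstructured covariance, fitted once to the level and once to the change.

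**Expected z with no change.** The residual SD is 0.32 × √(1 − 0.6²) = 0.256. The standard error is 0.256/√577 = 0.0107 or 0.256/√288 = 0.0151. For a geometric mean of 10, z ≈ 1/0.0107 ≈ 94 and 1/0.0151 ≈ 66.

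**Simulated results, no true change (60 runs per setting).**

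| n | Baseline geometric mean | Estimate as written (should be 1) | Mean z | Rejection as written |
|---|---|---|---|---|
| 577 | 5 | 5.02 | 66 | 100% |
| 577 | 10 | 10.01 | 95 | 100% |
| 577 | 20 | 19.87 | 122 | 100% |
| 288 | 5 | 5.03 | 47 | 100% |
| 288 | 10 | 9.95 | 66 | 100% |
| 288 | 20 | 19.97 | 88 | 100% |

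In every fit the two coefficients differed by b̄ to rounding error (about 5 × 10⁻¹⁴).

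**Other settings.**

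- True 30% fall from 10: the written model gives 6.9 (n=577) and 7.1 (n=288); the change model gives 0.69 and 0.71.
- True 20% rise from 10: the written model gives 12.0 and 12.1 and rejects in every run; the change model gives 1.20 and 1.21.
- No change, with the geometric mean of 10 pg/mL expressed in ng/mL (n=577): the written model gives 0.010, which reads as a 99% fall. The answer depends on the unit.
- Week 48 geometric mean of exactly 1 unit after a real 30% fall: the written model rejects in 5% (n=288) to 8% (n=577) of runs; the change model rejects in 100%.

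**Change as outcome, no true change, geometric mean 10 (3,000 runs).** The estimate is 1.00, and rejection is 7.3% (n=577) and 5.9% (n=288). The small excess over 5% arises because the estimated centring mean is treated as known.

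**The case against.** The strongest reply is that the intent is plain. The heading of 4.3.3, the estimand, the interpretation of the coefficients, the reported estimate and the description of the test all speak of change or ratio to baseline, as do Table 1, SAP 2.1 and Protocol 2.1.2. Only the phrase naming the dependent variable conflicts. If the outcome is taken to be the log10 ratio to baseline, the paragraph is coherent, so a few words were probably left out. The SAP is loose elsewhere too: the repeated-measures model in 4.4.2 never names its dependent variable. If the programming already uses the log ratio, the tests are right and only the text is wrong.

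The point about intent stands, but it does not rescue the specification. Where the SAP models a change elsewhere (4.3.2 and 4.4.3), it says so in defining the outcome. Section 4.3.3 has no sample code, unlike 4.3.2, and SAP section 5 says there is no supporting document. Nothing in the documents redefines the outcome, and the programming cannot be seen.

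Three narrower points also stand. The SAP does not write down the null value of the Wald test, so zero is the natural inference rather than a quotation. The unit pg/mL appears only for CSF NfL. And rejection regardless of the drug's effect requires a geometric mean clearly different from 1 unit.

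**Conclusion.** The concern holds. As written, the estimator for two confirmatory endpoints returns an adjusted geometric mean concentration instead of a ratio to baseline, and its Wald test does not address the null in SAP 2.1. The error factor is 10^b̄, the geometric mean of baseline NfL over all patients used for centring. This is an identity and needs no assumption.

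The size in practice rests on the assumed blood level. At 5 to 20 pg/mL both tests reject with certainty when nothing has changed, with z of about 47 to 122 across the two arm sizes. A second set of assumed variances (log10 SD 0.25, residual SD 0.18) gives z of about 66 to 123 at n=288 and the same 100% rejection. Only a geometric mean close to 1 unit would avoid this, and then a real fall would be missed. The effect on the testing sequence arises only if the primary and the first three secondary tests succeed and the text is programmed literally. The target itself is stated correctly; the model specification is what is wrong.

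**What to change.** In SAP 4.3.3, define the dependent variable as change from baseline in log10 NfL: log10 NfL at the visit minus log10 NfL at baseline. Keep visit, centred log10 baseline NfL, their interaction and the centred stratification factors, with no intercept, and state the null as Week 48 coefficient = 0. Then 10 to the power of that coefficient is the adjusted ratio to baseline, as Table 1 intends. Keeping the level as outcome and testing the Week 48 coefficient against the mean log10 baseline value gives the same estimate and test; the ratio is then 10^(coefficient − b̄).

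Confirm that the analysis program matches, and document the correction before anyone sees unblinded NfL results, so that it is not a change made in response to an implausible estimate. The cost is one phrase in the SAP and one derived variable, with no new data.

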## **4. STATISTICAL ANALYSES**

### **4.1 GENERAL CONSIDERATIONS**

All statistical hypotheses for the primary and secondary endpoints and treatment comparisons will be tested at the 5% significance level ( $\alpha=0.05$ ) against two-sided alternatives.

All primary and secondary efficacy endpoints will be stratified by region, age at screening, baseline EDSS and baseline body weight for analysis. The regional stratifications are United States and ROW. The age categories are  $\leq 45$  years and  $> 45$  years. The EDSS categories are  $< 4.0$  and  $\geq 4.0$ . The body weight categories are  $< 75$  kg and  $\geq 75$  kg.

The baseline for the primary endpoint is the date of randomization. The baseline value of the endpoint, e.g., EDSS, T25FWT and 9-HPT values, is the most recent value up to and including the date of randomization but before first infusion of study drug. A subject with delayed dosing may receive the first dose 2 weeks after the baseline visit; if an EDSS, T25FW or 9-HPT score is recorded between the randomization date and the date of the first dose, this value will be considered as a post-baseline assessment.

FAS will be used in the analysis of the primary and secondary estimands, and exploratory efficacy endpoints. Safety analysis set (SAS) will be used to summarize safety data. For analysis purposes, the time of treatment discontinuation will be defined as 24 weeks after the last dose prior to the date of treatment discontinuation recorded in the electronic Case Report Form (eCRF).

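### The within-arm NfL tests treat the estimated baseline mean as known, so for the population mean change the standard error is too small and the tests run above 5%

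*SAP*

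**What the plan says.** SAP 2.1 puts two within-arm NfL hypotheses fourth and fifth among ten secondary tests: "The secondary efficacy estimands will be tested in the hierarchical order listed below". The null is "There is no change in NfL from baseline at Week 48 within the higher or approved dose of ocrelizumab arms". The level comes from SAP 4.1: "All statistical hypotheses for the primary and secondary endpoints and treatment comparisons will be tested at the 5% significance level", two-sided.

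SAP 4.3.3 sets the target: "The estimand is the mean change from baseline in NfL at Week 48 for RMS patients", within each arm. For the estimator, "The MMRM will be fitted to each treatment arm separately". The model has no intercept. It has terms for visit (Weeks 12, 24, 48), baseline log10 NfL, their interaction, and the stratification factors. On centring: "The baseline covariates in the model will also be centered, i.e., the mean of the variable over all patients in the study" is subtracted from each covariate. The Week 48 coefficient is back-transformed to a ratio, and "The statistical significance of the estimated mean change from baseline will be calculated by using the Wald test".

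Two further details of SAP 4.3.3 matter. It describes the visit coefficients as mean changes given the baseline covariates. It also names log10 NfL itself, not its change, as the dependent variable. No term for the sampling error of the centring mean is described.

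**The concern.** Each test compares Week 48 with baseline in the same patients of one arm. If the sampled baseline mean is high by chance and the slope on baseline is below 1, the fitted Week 48 value at that mean shows a fall even when the RMS population has none. That is regression to the mean, and a valid standard error for the population change must allow for it. In a between-arm contrast evaluated at a common centring point the term cancels. In a within-arm test it does not.

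At stake are the error rate of two confirmatory tests and the width of the two reported intervals. CDP12, cCDP48, SDMT, MSWS-12 and brain volume are gated behind these tests.

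**Working it through.** **Inputs.** From the SAP: 5% two-sided (4.1), 2:1 allocation (1.3.1) and N = 865 randomized (2.2), hence about 577 and 288 per arm. Not in the documents, so assumed over a range: the correlation rho between baseline and Week 48 log10 NfL in blood, and k = SD at Week 48 / SD at baseline. The slope is b = k·rho. I assume normal log10 NfL and complete data, and take the outcome as change in log10 NfL.

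**The plan's figure.** The figure to check is the 5% level. If the null is set at the observed centring mean, simulation (20,000 trials per setting, rho 0.3 to 0.9, k = 1) gives 4.8% to 5.5%. The plan's level is therefore reproduced under the conditional reading.

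**Population reading.** Write the change for patient i as δ + (b-1)(B_i - μ) + e_i. The coefficient at the centring point estimates δ + (b-1)(all-patient baseline mean - μ). In units of the baseline variance:

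- model variance = k²(1-rho²)/n_arm
- omitted variance = (k·rho-1)²/N
- true level = 2Φ(-1.96 × √[model/(model + omitted)])

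**Worked case, k = 1, rho = 0.5.**

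- Higher dose: 0.75/577 = 0.001300; omitted 0.25/865 = 0.000289; variance ratio 1.222; 1.96/√1.222 = 1.773; level 7.6%.
- Approved dose: 0.75/288 = 0.002604; same omitted term; ratio 1.111; level 6.3%.

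**Equal SDs (k = 1), higher/approved dose.**

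| rho | Formula | Simulation |
|---|---|---|
| 0.3 | 9.3% / 7.1% | 9.2% / 7.3% |
| 0.5 | 7.6% / 6.3% | 7.6% / 6.4% |
| 0.7 | 6.4% / 5.7% | 6.5% / 5.8% |
| 0.9 | 5.4% / 5.2% | 5.5% / 5.6% |

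A three-visit unstructured model with stratification factors (4,000 trials) gave 7.5%/6.8% at rho 0.5 and 6.3%/5.9% at rho 0.7.

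**Smaller spread at Week 48 (rho = 0.5).** k = 0.8: 11.0%/8.0%. k = 0.7: 14.0%/9.6%. k = 0.6: 18.7%/12.2%. Over rho 0.3-0.7 and k 0.6-1.0 the level runs 6.4-20.3% / 5.7-13.1%, and the model SE is 65-95% / 77-97% of the true SE. High correlation removes the problem only when the SDs are also equal: at rho 0.9 and k = 0.8 the level is 10.1%/7.5%.

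**Repairs checked (k = 1).** Adding the omitted term to the squared SE gave simulated levels of 4.9% to 5.4%. A plain paired test gave 4.8% to 5.4%.

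**Literal coding.** With the level as outcome, the Week 48 coefficient is mean log10 NfL, and the Wald test asks whether the geometric mean is 1 unit. Assume a geometric mean of 5 to 20 units, rho 0.5, and SD 0.32 borrowed from the CSF substudy (Protocol Appendix 18, Section 6.1). Then z is about 43 to 113, and the null is rejected almost surely whether or not NfL changed.

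**The case against.** **The SAP can be read conditionally.** It describes the coefficients as given the baseline covariates, conditioning is the ordinary standard error for an adjusted mean, and on that reading the test is nominal. This stands as a limit on the claim. It does not dispose of it, because the estimand sentence speaks of RMS patients and the null in SAP 2.1 carries no conditioning. A reader might infer that the tests exceed 5% on any reading; the documents do not support that.

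**The large rates need k well below 1.** No document gives k. The argument for k < 1 is that past relapses raise and spread baseline NfL. But a raised baseline that then settles makes the mean fall, so the null is false and type I error does not apply. Entry also requires no relapse in the 30 days before screening and neurological stability (Protocol 4.1.1). A reader might infer error rates of 10-20%; these rest on an assumption and should not be the headline. The same percentages are, however, non-coverage rates of the nominal 95% interval, and those do not depend on the null.

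**The consequence is small.** The tests count only if the primary, cCDP24, CIT25FWT12 and cPIRA12 all succeed. The Protocol (3.1.2) already reports that NfL in CSF falls on ocrelizumab, so a true null is unlikely. With the borrowed SD of 0.32, the higher-dose half-width on the ratio is about 5.3% stated against 5.9% correct at k = 1, rho 0.5, and 3.5% against 5.4% at k = 0.6, rho 0.3. This stands: the main effect is on reported precision, not on the likely decision.

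**Conclusion.** The point holds for the population mean change. The standard error omits the variance of the centring mean, so both tests run above 5% and both intervals are too narrow whenever b differs from 1. With equal SDs the excess is modest: 4.3 and 2.1 percentage points (higher and approved dose) at rho 0.3, 2.6 and 1.3 at rho 0.5, and under half a point at rho 0.9. Levels up to about 20%/13% need k well below 1.

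The sizes rest on an unstated rho and k, on complete data, and on the outcome being a change. They do not describe the model as literally written, where the level coding is the larger defect and must be corrected first. A reader might also infer that a positive NfL result could not be trusted, or that the between-arm comparisons are affected. Neither follows: a large fall would be significant with either standard error, and this mechanism does not reach the between-arm contrasts.

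**What to change.** In SAP 4.3.3:

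1. Make the dependent variable the change in log10 NfL.
2. State that inference is for the population mean change.
3. Keep the MMRM centred at the all-patient mean, and add (b-1)² × Var(baseline)/N to the squared SE of the Week 48 coefficient before the Wald test and interval. Here b-1 is the fitted Week 48 slope of change on baseline.

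This needs about a paragraph of wording, a few lines of code and no new data. The price is wider intervals: about 6-54% in the higher-dose arm and 3-30% in the approved-dose arm over rho 0.3-0.7 and k 0.6-1.0.

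A valid alternative is a per-arm MMRM with baseline as a response (Weeks 0, 12, 24, 48), testing the Week 48 minus Week 0 contrast. It also cures the level coding. It gives up the gain from centring on all patients, so with complete data its intervals are about 8.5-75% wider than the planned ones in both arms. Only its complete-data paired form was simulated here.
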